Primary Endpoint(s)	
The primary safety endpoint is freedom from major adverse events (MAE) at 30 days or during hospitalization if this exceeds 30 days. Major adverse events include death, bowel ischemia, myocardial infarction, paraplegia, renal failure, respiratory failure, and stroke.
 
The primary effectiveness endpoint is the proportion of the study subjects with treatment success at 1 year. Treatment success is defined as a composite of technical success and freedom from the following:
 
 • Aneurysm enlargement i.e., $\geq 5\text{mm}$ as compared to any previous CT measure using orthogonal (i.e., perpendicular to the centerline) measurements • Aneurysm rupture • Aneurysm-related mortality • Conversion to open repair • Secondary intervention for migration, Type I and III endoleaks, device integrity failure (e.g., fracture), and patency-related events (i.e.,

	device component stenosis or occlusion and embolic events)
Secondary Endpoints	
Secondary endpoints include:
 
 • Technical success and the individual components of technical success: 
 ○ Successful delivery ○ Deployment at the intended implantation site ○ Patency of all endovascular graft and stent components ○ Absence of device deformations requiring unplanned placement of an additional device ○ Absence of inadvertent covering of aortic branch vessels ○ Successful withdrawal • Freedom from the individual components of the primary safety endpoint at 30 days: 
 ○ Death ○ Bowel ischemia ○ Myocardial infarction ○ Paraplegia ○ Renal failure

	
 ○ Respiratory failure ○ Stroke ● Freedom from paraparesis at 30 days ● The following at each follow-up interval: 
 ○ Treatment success and the individual components of treatment success including freedom from the following: 
 – Aneurysm enlargement – Aneurysm-related mortality – Aneurysm rupture – Conversion to open repair – Secondary intervention for migration, type I and III endoleaks, device integrity failure (i.e., fracture), and patency-related events (i.e., device stenosis or occlusion and embolic events). – Renal failure – All-cause mortality – Endoleaks – Device integrity failure (e.g., fracture) – Patency-related events (i.e., device stenosis or occlusion and embolic events)
--	--

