4.4.3 Study Endpoints

The primary safety endpoint is freedom from major adverse events (MAE) at 30 days or during hospitalization if this exceeds 30 days.

Major adverse events include death, bowel ischemia, myocardial infarction, paraplegia, renal failure, respiratory failure, and stroke.

The primary effectiveness endpoint is the proportion of the study subjects with treatment success at 1 year. Treatment success is defined as a composite of technical success and freedom from the following:

- Aneurysm enlargement i.e., $\geq 5\text{mm}$ as compared to any previous CT measure using orthogonal (i.e., perpendicular to the centerline) measurements
- Aneurysm rupture
- Aneurysm-related mortality
- Conversion to open repair
- Secondary intervention for migration, Type I and III endoleaks, device integrity failure (e.g., fracture), and patency-related events (i.e., device component stenosis or occlusion and embolic events)

Secondary endpoints include:

- Technical success and the individual components of technical success:
 - Successful delivery
 - Deployment at the intended implantation site
 - Patency of all endovascular graft and stent components
 - Absence of device deformations requiring unplanned placement of an additional device
 - Absence of inadvertent covering of aortic branch vessels
 - Successful withdrawal
- Freedom from the individual components of the primary safety endpoint at 30 days:
 - Death
 - Bowel ischemia
 - Myocardial infarction
 - Paraplegia
 - Renal failure
 - Respiratory failure
 - Stroke
- Freedom from paraparesis at 30 days
- The following at each follow-up interval:
 - Treatment success and the individual components of treatment success including freedom from the following:
 - Aneurysm enlargement
 - Aneurysm-related mortality

- Aneurysm rupture
- Conversion to open repair
- Secondary intervention for migration, type I and III endoleaks, device integrity failure (i.e., fracture), and patency-related events (i.e., device stenosis or occlusion and embolic events).
- Renal failure
- All-cause mortality
- Endoleaks
- Device integrity failure (e.g., fracture)
- Patency-related events (i.e., device stenosis or occlusion and embolic events)
- Other device-related events

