4.4.6 Sample Size Justification

The sample size for the feasibility study is limited to 15 patients, as this is adequate to provide preliminary clinical safety data and effectiveness of the device. We plan for 6 subjects to enroll in the primary arm, and 9 subjects to be enrolled under extended criteria. The device, while novel, has been evaluated in a clinical setting and has initially demonstrated both safety and effectiveness. The limited sample size allows adequate patient data to be collected under a controlled protocol without exposing a large patient population to the risk associated with a novel device design. The safety and effectiveness data collected in this study will be pooled with other physician sponsored investigational device exemptions (PS-IDEs) evaluating the Visceral Manifold System and should be sufficient to develop an appropriate pivotal study.

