4.4.7 Data Presentation and Analysis Plan

The primary purpose of this study is to evaluate the safety of this device as there are no or very limited devices and clinical options available for this patient population. The primary safety endpoint of this study is freedom from major adverse events (MAE) at 30 days or during hospitalization if this exceeds 30 days. Major adverse events include death, bowel ischemia, myocardial infarction, paraplegia, renal failure, respiratory failure, and stroke. The primary safety endpoint will be analyzed to determine statistical significance when compared to a target performance goal. A literature review of outcomes of open surgical repair was used to create the performance goal as there is not a comparable endovascular option to use for analysis. The performance goal was selected based on the range of subjects experiencing a major adverse event at 30 days. The range was calculated based on assumptions of the minimum and maximum number of subjects experiencing at least one MAE in the historical open surgical repair group (Table 6). Based on the literature reviewed and the above assumptions the range of subjects experiencing at least one MAE in the open surgical repair group is 30.5% to 77.4%.

The primary effectiveness endpoint is the proportion of the study subjects with treatment success at 1 year. The data will be presented as quality outcomes, with the number of study subjects who experience treatment success compared to the overall patient population.

Additionally, data outcomes from this study will be entered into a common vascular database so that data can be pooled with other PS-IDEs. This would provide consistent reporting across the PS-IDEs. Additionally, the PS-IDEs will be evaluating the same device and endpoints to allow for a pool-ability of data across the sites.

The data will be separated into two separate study arms: primary study arm and expanded selection arm.

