4.9 Definitions

Aortic aneurysm enlargement: $\geq 5\text{mm}$ as compared to any previous CT measure using orthogonal (i.e., perpendicular to the centerline) measurements

Aortoiliac aneurysm: aneurysm of the abdominal aorta and including one or both of the iliac arteries

Aneurysm-related mortality:

Death occurring within 30 days or during hospitalization following the index procedure, unless there is evidence of accidental or self-inflicted death;

Death occurring within 30 days or during hospitalization following conversion to open repair or a secondary intervention for migration, Type I and III endoleaks, device integrity failure (e.g., fracture), or patency-related events (i.e., device stenosis or occlusion and embolic events), unless there is evidence of accidental or self-inflicted death;

Death occurring within 30 days or during hospitalization for a complication of the aneurysm or a complication associated with the device, such as:

- aortic rupture
- fistula formation (e.g., aorto-enteric)
- embolization
- malperfusion of organ(s) or limb(s)

Arterial fistula formation: formation of an abnormal connection or passageway between an artery and adjacent structures

Conversion to Open, Early: any open repair within 30 days of the index procedure involving the vasculature in the abdomen and/or pelvis.

Conversion to Open, Late: any open surgical repair involving stentgraft removal after 30 days post index procedure

Chronic Obstructive Pulmonary Disease (COPD): forced expiratory volume (FEV1) < 1.0 liter or receiving home oxygen

Crawford Type IV TAAA: aneurysmal dilatation originating within 5cm of the celiac artery

Disabling stroke: Modified Rankin Score MRS >2

Distal landing zone: aortic fixation site furthest from the heart

Embolization: dislodging of an upstream particle that travels downstream causing blockage of free flow further downstream. Embolization could result in malperfusion

Embolus: blood clot that forms at one location (presumably from the aneurysmal sac, aortic neck, or adjacent vessels) and is dislodged to another location resulting in ischemic changes

Emergent: an aneurysm requiring immediate treatment

Endoleak:

Type I: leak occurring at the proximal or distal fixation site, including leakage around fenestrations

Type Ia: leak occurring at the proximal fixation zone of the stent-graft

Type Ib: leak occurring at the distal fixation zone of the stent graft

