Paraparesis: spinal cord ischemic event resulting in partial neurologic deficit in the lower extremities

Parietal arteries (branches): inferior phrenic, lumbars and middle sacral arteries

Patency: the state of a vessel that has unimpeded flow into and out of the vessel

Proximal landing zone: the aortic fixation site closest to the heart

Proximal fixation length: the aortic fixation site measured from the proximal edge of the graft to the start of the aneurysm

Renal insufficiency: rise in serum creatinine of more than 50% above pre-procedure level which results in a serum creatinine >2.0 mg/dl that does not spontaneously resolve

Technical success:

- successful delivery (i.e., ability to deliver the implant to the intended implantation site, without the need for unanticipated corrective intervention related to delivery);
- successful and accurate deployment, defined as:
 - deployment of the endovascular stent-graft at the intended implantation site;
 - patency of all endovascular graft and stent components; absence of device deformations (e.g., kinks, stent eversion, mal-deployment, misaligned deployment) requiring unplanned placement of an additional device;
 - absence of inadvertent covering of aortic branch vessels; and
- successful withdrawal (i.e., successful withdrawal of the delivery system, without need for unanticipated corrective intervention related to withdrawal)

Thrombus: a blood clot that forms due to injury of a vessel. If the thrombus becomes dislodged and travels it is referred to as an embolus

Treatment success: a composite of technical success and freedom from the following:

- aneurysm enlargement i.e. ≥ 10 -mm as compared to any previous CT measuring orthogonal (i.e., perpendicular to centerline) measurements
- aneurysm-related mortality
- aneurysm rupture

- conversion to open repair
- secondary intervention for migration, type I and III endoleaks, device integrity failure (i.e., fracture), and patency-related events (i.e., device stenosis or occlusion and embolic events)
- Renal failure

Type B – Chronic Dissection: a dissection that takes off distal to the left subclavian artery that is greater than 30 days old

Type B – Subacute Dissection: a dissection that takes off distal to the left subclavian artery that is 15-30 days old

Urgent: An aneurysm requiring repair within 1 week

Visceral arteries (branches): celiac, superior mesenteric, inferior mesenteric, renal arteries

5. Manufacturing Information

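### Treatment success at 1 year, the primary effectiveness endpoint, has two incompatible definitions: the enlargement threshold is 5 mm or 10 mm, and renal failure is left out or included

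*Combined protocol and SAP*

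**What the plan says.** The Synopsis (Primary Endpoint(s)) and section 4.4.3 define treatment success as technical success plus freedom from five items. The first is "Aneurysm enlargement i.e., $\geq 5\text{mm}$ as compared to any previous CT measure using orthogonal" measurements. The others are rupture, aneurysm-related mortality, conversion to open repair, and secondary intervention for specified causes. Renal failure is not among them.

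Section 4.9 has two relevant entries. The stand-alone one agrees with the lists above: "Aortic aneurysm enlargement: $\geq 5\text{mm}$ as compared to any previous CT measure using orthogonal" measurements. The Treatment success entry does not. Its first item is "aneurysm enlargement i.e. ≥ 10 -mm as compared to any previous CT measuring orthogonal (i.e., perpendicular to centerline) measurements", and its sixth and last is renal failure.

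The secondary endpoints in the Synopsis and section 4.4.3 contain a further list, introduced as "Treatment success and the individual components of treatment success including freedom from the following". It gives no threshold. It names renal failure sixth, then runs on through outcomes that neither definition counts as components: "Renal failure – All-cause mortality – Endoleaks" and others.

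On analysis, section 4.4.7 says of the effectiveness endpoint: "The data will be presented as quality outcomes, with the number of study subjects who experience treatment success compared to the overall patient population". On pooling, the same section says: "Additionally, the PS-IDEs will be evaluating the same device and endpoints to allow for a pool-ability of data across the sites".

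**The concern.** A primary endpoint needs one rule that classifies every subject the same way, whoever applies it. Here the endpoint section and the definitions section give different rules. A person coding outcomes from section 4.9 would produce a different success count from one working from section 4.4.3.

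Three things are at stake. First, the arms have 6 and 9 subjects, so one reclassified subject visibly changes the headline rate. Second, the study is nonrandomized and the sponsor is also the principal investigator. If the choice is left until outcomes are known, it can be made, or appear to be made, with the results in view. Third, the data are meant to be pooled with other studies on common endpoints, and a site that holds two definitions cannot show that its endpoint matches theirs. The conflict also carries into treatment success at every follow-up interval, not only at 1 year.

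**Working it through.** The plan gives no target, sample size or power for effectiveness, so there is no stated figure to reproduce. The check is a comparison of the texts, followed by the consequences for classification.

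**Step 1. The texts side by side**

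| Place | Enlargement threshold | Renal failure |
|---|---|---|
| Synopsis, primary endpoint | ≥5 mm | not listed (five items) |
| 4.4.3, primary endpoint | ≥5 mm | not listed (five items) |
| 4.9, Aortic aneurysm enlargement | ≥5 mm | not applicable |
| 4.9, Treatment success | ≥10 mm | listed (six items) |
| Synopsis and 4.4.3, secondary lists | none given | listed sixth; list then continues |

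The first six items of the secondary lists follow the order of the 4.9 Treatment success entry. That suggests renal failure was meant as a component. It does not settle the matter, because the same lists go on to items such as all-cause mortality. Counting places does not resolve both halves: 5 mm appears in three of four places, whereas renal failure is absent from the two primary lists but present in the two secondary lists and in 4.9.

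**Step 2. Classification of a subject with technical success and no other failing item**

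| Subject | Synopsis and 4.4.3 | 4.9 Treatment success |
|---|---|---|
| Growth 5 to <10 mm, no renal failure | failure | success |
| Renal failure, growth <5 mm | success | failure |
| Growth 5 to <10 mm and renal failure | failure | failure |
| Growth ≥10 mm | failure | failure |

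Let A be the number in the first row, B the number in the second, and n the denominator. Then

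rate under 4.9 − rate under 4.4.3 = (A − B)/n.

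The sign depends on whether A or B is larger. If A = B, the two rates agree while counting different people as successes.

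**Step 3. Size per subject** (arm sizes from section 4.4, all subjects evaluable)

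- Primary arm: 1/6 = 16.7 points
- Expanded arm: 1/9 = 11.1 points
- Both arms: 1/15 = 6.7 points

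**Step 4. Can A or B be estimated?**

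*Growth (A).* No growth rate after repair with this device is given. Section 3.4.2 cites a study of another branched device with no growth over twelve months. Section 3.2 gives 2–4 mm per year without repair. If a sac that was not excluded kept that pace, it would grow 2–4 mm by 12 months, 4–8 mm by 24 and 6–12 mm by 36. Eligibility can also rest on growth of at least 0.5 cm in 6 months. At exactly that pace, such a sac would reach 5 mm at 6 months and 10 mm at 12. These are assumptions about unexcluded sacs. They show that A could be zero at 1 year or not, and no more.

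*Renal failure (B).* Table 7 reports 1/20 at 30 days in subjects meeting the primary criteria. Section 3.9 reports 6/14 in subjects outside the criteria, but counts temporary or permanent cases and does not tie them to the dialysis or hemofiltration definition in 4.9. Neither is a 1-year rate, and neither can be projected to this study.

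**The case against.** The strongest reply is that little depends on this. The study is a 15-subject feasibility study, section 4.4.7 names safety as its main purpose, and effectiveness is a descriptive count with no performance goal. The sample-size calculation (46 pooled subjects) concerns the 30-day adverse event rate and does not use treatment success. Either threshold should be computable from the same scheduled CT scans. Renal failure within 30 days, or during a longer hospital stay, already counts in the primary safety endpoint, and renal failure is also reported separately at follow-up. The growth difference may affect nobody at 1 year.

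All of that stands, and it limits the consequences. It does not tell a reader which rule produced the composite.

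Two further points also stand in part. The shifts of 16.7, 11.1 and 6.7 points assume that everyone is evaluable. They show how much one subject counts in small arms and do not measure how many subjects the conflict affects. The harm to pooling is not demonstrated either, since the other studies' wording is not in these documents.

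The conflict cannot be put down to text extraction. The wording around the 10 mm figure also differs, as do the number and order of the items. Nor is it superseded text in a change log.

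**Conclusion.** The concern holds and should be corrected. The current text gives two incompatible rules for a named primary endpoint, and nothing ranks one above the other. Subjects whose only failing item is growth of 5 to <10 mm, or only renal failure, are classified in opposite ways. The size is known only per subject, as shown in the working and on the assumption of full enrolment and follow-up. With missing 1-year data and a smaller denominator, each subject would count for more. The number of subjects affected and the net direction cannot be determined from the documents. The primary safety hypothesis, its significance level and its sample size are untouched.

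**What to change.** Before any 1-year outcome is reviewed, amend the wording as follows:

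- State one enlargement threshold and use it in the Synopsis, section 4.4.3 and both entries in section 4.9. The documents do not show which was intended, so the sponsor must decide and record the decision.
- State one component list for treatment success, with an explicit yes or no on renal failure, in the same places.
- In the secondary lists, mark which items are components of treatment success and which are stand-alone outcomes.
- Compare the chosen definition with those of the other physician-sponsored studies. If theirs differ, agree one definition for the pooled data.

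The cost is a wording amendment plus that comparison. No test, sample size or data collection in this study changes. The reported success rate may move in either direction.
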